4.2. Number of cases, grouping and study centers

According to the China National Stroke Registry (CNSR), 39.59% of patients with NIHSS Page 7 of 76

score of 4–22 at admission had mRS \leq 1 at 3 months. Assuming a 40% proportion of patients with mRS \leq 1 at 90 days in the control group and a 47% proportion in the treatment group, with an equal ratio design, and utilizing PASS 2008 to calculate the required sample size, with α = 0.05 (two-sided test) and β = 0.2 (test power 80%), the calculated sample size for both the treatment and control groups is 787 cases. To account for potential dropouts in clinical studies, an additional 20% of the sample size is added. Therefore, a total of 1,968 patients are planned to be included in this study.

Patients will be allocated in a 1:1 ratio to the treatment group and the control group, and the study is planned to be conducted at 50 centers nationwide.

5. Study Population

Patients entering the study must meet all the inclusion criteria listed below and must not meet any of the exclusion criteria. In addition to the criteria listed below, any medical conditions or use of prohibited medications during the standard treatment that are considered contraindications will also be grounds for excluding patients from the study.

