9.1 Efficacy determination criteria

9.1.1 Primary efficacy assessment

• The proportion of patients with improvement in activities of daily living 90 days after treatment (mRS score ≤1): mRS ≤1 indicates complete or substantial recovery of activities of daily living, representing a favorable prognosis. Comparison of the proportion of patients with favorable prognosis in the treatment group and the control group 90 days after randomization;

9.1.2 Secondary efficacy assessment:

- Improvement in neurological deficit, i.e., the proportion of patients with NIHSS ≤1 or NIHSS improved by 4 points or more: NIHSS score ≤1 or reduction of ≥4 points is considered effective; compare the proportion of effective and ineffective patients and continuous changes of NIHSS in the treatment group and the control group after 90 days of randomized treatment;
- Proportion of patients with BI index ≥85: BI score ≥85 indicates the ability to live
 independently. Compare the proportion of patients able to live independently between
 the treatment group and the control group 90 days of randomized treatment, as well as
 continuous changes in BI scores between the two groups;
- Disability rate, defined as the proportion of patients with an mRS score ≥3: An mRS score ≥3 indicates the inability to live independently. Compare the percentage of disabled patients between the treatment group and the control group 90 days of

randomized treatment:

- Continuous changes in mRS scores: Compare the changes in mRS scores between the treatment group and the control group at different visit points, including baseline, 7 d, discharge, and 90 d;
- Incidence of ischemic cerebrovascular events during the follow-up period: The
 proportion of ischemic stroke or TIA within 90 days of randomized treatment, or
 newly occurring ischemic lesions detected on MRI at the last visit, will be assessed as
 a group or separately;
- Incidence of combined vascular events during the follow-up period: The cumulative
 incidence of newly occurring combined vascular events within 90 days of randomized
 treatment will be assessed as a group or separately;

Definition of combined vascular events: Consist of any type of stroke (ischemic stroke, hemorrhagic stroke), TIA, myocardial infarction, and vascular death.

Vascular death: Hemorrhagic death of any organ or fatal pulmonary embolism.

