5.2 Secondary effect index

1. Improvement of neurological deficits (ratio of NIHSS≤1 or improve 4 score or more);

Improvement of neurological deficits (ratio of NIHSS≤1 or improve 4 score or more): It is effective for NIHSS≤1 or reducing 4 points or more; compare the ratio of efficacy and inefficacy and the continuous change of NIHSS between treatment group and control group 90 days after random treatment;

2. Improvement of daily life ability (ratio of BI index ≥85);

Ratio of patients with BI index≥85: BI score≥85 indicates the patient with ability of independent living; compare the ratio of patient with ability of independent living and continuous change of BI between treatment group and control group at 90 days after random treatment;

3. Disability rate (ratio of mRS score \geq 3)

mRS≥3 indicates the patient without self-care ability; compare the disability rate between treatment group and control group at 90 days after random treatment;

4. Continuous change of mRS score

Compare change of mRS score at baseline, 7d, discharge day and 90d between treatment group and control group;

5. Incidence of ischemic cerebrovascular diseases during follow-up period;

Ratio of ischemic stroke or TIA within 90 days after random treatment, or ratio of new ischemic focus detected by MRI during the last visit, and take this kind of patients as a group for evaluation or respective evaluation:

6. Incidence of combined vascular events during follow-up period;

Accumulated ratio of patients having newly combined vascular events within 90 days after random treatment;

Definition of combined vascular events: Include any type of stroke (ischemic stroke and hemorrhagic stroke), TIA, myocardial infarction and vascular death.

Vascular death: Hemorrhagic death or fatal pulmonary embolism of any organ.

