6.1.1 Full analysis set (FAS)

Full analysis set (FAS) or modified intention-to-treat (ITT): Set of all the patients who underwent randomization, given any treatment, and underwent any posttreatment assessment. When main indexes of curative effect are missing, the set should be supplemented with last observation carried forward (LOCF) on the basis of intention to treat (ITT). Comparability analysis and the missing value of secondary effect indexes don't need data-carry-forward. Take analysis on actual data in FAS.

FAS population is the main population for curative evaluation in this study.

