6.2.4 Efficiency evaluation

Baseline efficiency: Describe the baseline of each curative index, and comparison between groups should be made in accordance with general condition. Modified Rankin (mRS) score is regarded as ranked data, and should be compared with Wilcoxon rank sum test. NIHSS score should be regarded as quantitative data and ranked data (4-7 points, 8-14 points and 15-22 points) for description and comparison; BI score as quantitative data and enumeration data (<85 points, ≥85 points) for description and comparison.

Primary efficiency indexes:

PP analysis and FAS analysis should be performed at the same time; evaluation on patients with modified Rankin (mRS) score≤1 should be mainly conducted ontaken at day 90 day (PP set) and the time for suspending and drop-out (FAS set). Primary indexes should be compared between the two groups with CMH-γ2 method for controlling central effect.

Superiority test is adopted for primary indexes, and the hypotheses under test are as follows:

$$H_0$$
: $\pi_{\text{treatment group}} - \pi_{\text{control group}} \le 0$

$$H_1: \pi_{\text{treatment group}} - \pi_{\text{control group}} > 0$$

$$\alpha = 0.025_{\text{(one-sided)}}$$

The treatment group is superior to control group, if H0 is rejected under α level, or lower limit of 95% Cl for difference of retention rate between the two groups is higher than 0. Take sensitivity analysis on primary efficiency indexes with modified Rankin (mRS) score≤2 points as the limit.

Other secondary indexes can be statistically analyzed in accordance with methods for primary indexes.

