7.3.6 Secondary effect index – continuous change of mRS score

Table 7.3.6.1 Continuous change of mRS score (FAS)

Item	Index	Treatment group	Control group
	N(Missing)		
Baseline mRS score	Mean(SD)		
	Median		
	Q1,Q3		
	Min, Max		
	Statistics		
	P value		
	N(Missing)		
mRS score at 7 days after treatment	Mean(SD)		
•	Median		
	Q1,Q3		
	Min, Max		
	Statistics		
	P value		
	N(Missing)		
Change of mRS score at 7 days after treatment comparing with baseline	Mean(SD)		
r	Median		
	Q1,Q3		
	Min, Max		
	Statistics		
	P value		
	95%CI		
	Statistics		
	P value		
	N(Missing)		
mRS score at discharge day	Mean(SD)		
5	Median		
	Q1,Q3		
	Min, Max		
	Statistics		
	P值 P value		
	N(Missing)		
Comparison of mRS score at discharge			
day comparing with baseline	,		
	Median		
	Q1,Q3		
	Min, Max		
	Statistics		

Study No.: Document No.:

Item	Index	Treatment group	Control group
	P value		
	95%CI		
	P value		
	N(Missing)		
mRS score at 90 days after treatment	Mean(SD)		
	Median		
	Q1,Q3		
	Min, Max		
	Statistics		
	P value		
	N(Missing)		
Changes of mRS score at 90 days after	er Mean(SD)		
treatment comparing with baseline			
	Median		
	Q1,Q3		
	Min, Max		
	Statistics		
	P value		
	95%CI		
	Statistics		
	P value		

Table 7.3.6.2 Continuous change of mRS score (PPS)

The same as above

7.3.7 Secondary effect index – incidence of ischemic cerebrovascular diseases during follow-up period Table 7.3.7.1 Inter-group comparison of incidence of ischemic stroke within 90 days after treatment

		FAS		PPS	
		Treatment		Treatment	
Item	Index	group	Control group	group	Control group
	With n(%)				
	Without n(%)				
Have ischemic stroke within	N (Missing)				
90 days after treatment					
	Statistics				
	P value				

Table 7.3.7.2 Inter-group comparison of TIA incidence within 90 days after treatment

The same as above

Table 7.3.7.3 Inter-group comparison of ratio of new ischemic focus detected by MRI at last visit

		FAS		PPS	
		Treatment		Treatment	_
Item	Index	group	Control group	group	Control group
	With n(%)				_
	Without n(%)				
New ischemic focu	s detected N (Missing)				
by MRI at the last v	risit				
	Statistics				
	P value				

Table 7.3.7.4 Inter-group comparison of incidence of ischemic cerebrovascular disease during follow-up period

		FAS		PPS	
		Treatment		Treatment	
Item	Index	group	Control group	group	Control group
	With n(%)				
Have ischemic cerebrovascular disease during visit	Without n(%)				
	N (Missing)				
	Statistics				
	P value				

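### The two 90-day vascular event endpoints are analysed as simple proportions, with no censoring method and no rule for patients who leave event-free before Day 90

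*Combined protocol and SAP*

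**What the plan says.** SAP 5.2 defines two event endpoints over 90 days. Combined vascular events are the "Accumulated ratio of patients having newly combined vascular events within 90 days after random treatment". Ischaemic cerebrovascular disease is the "Ratio of ischemic stroke or TIA within 90 days after random treatment", or a new ischaemic focus on MRI at the last visit. Protocol 9.1.2 describes the first as the cumulative "incidence of newly occurring combined vascular events within 90 days of randomized" treatment, without naming an estimator.

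On method, SAP 6.2.4 says "Other secondary indexes can be statistically analyzed in accordance with methods for primary indexes", which means the CMH chi-square controlling for centre. Table 7.3.7.1 ("Inter-group comparison of incidence of ischemic stroke within 90 days after treatment") sets the layout for the event tables in SAP 7.3.7 and 7.3.8: counts and percentages with and without the event, a missing count, a statistic and a P value.

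On missing data, SAP 6.1.1 says that "the missing value of secondary effect indexes don't need data-carry-forward" and adds "Take analysis on actual data in FAS".

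On expected loss, protocol 4.2 says "To account for potential dropouts in clinical studies, an additional 20% of the sample size is added".

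Neither document gives a time-to-event method, a censoring rule or a denominator rule for these endpoints.

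**The concern.** An event is seen only while the patient is followed. Take a patient who is lost event-free on Day 14. The table offers two places:

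- *Without* credits 76 unobserved days as event-free, so the incidence is too low.
- *Missing* removes the patient, while someone who left after an event stays in the numerator and the denominator, so the incidence is too high.

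Neither gives the 90-day cumulative incidence that the protocol names, and the plan leaves the choice to the analyst. At stake are the absolute incidences of two secondary endpoints and their clinical components. If the arms lose patients at different rates, the comparison is at stake as well.

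**Working it through.** **The plan's own figure.** For 40% v 47%, two-sided α = 0.05 and 80% power, the pooled formula without continuity correction gives 787 per arm, and 787 / 0.80 = 984 per arm, 1,968 in total. Both match SAP 4.4, so the 20% is a true dropout fraction.

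**Assumed inputs** (the documents give none of these):
- True 90-day risk R = 8%.
- Risk by day t: F(t) = 1 - (1 - R)^((t/90)^k), with k = 1 (constant hazard) or k = 0.6 (early-peaking hazard).
- A fraction L is lost independently of risk, either between Day 7 and Day 21 (early) or evenly over Days 0-90.

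Let E be the mean of F at the time of loss.
- *Without*: (1 - L)R + L·E
- *Missing*: [(1 - L)R + L·E] / [(1 - L) + L·E]

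Example with L = 0.20, k = 1 and even loss, so E = 0.0406. *Without* = 0.064 + 0.0081 = 7.2%. *Missing* = 0.0721 / 0.8081 = 8.9%.

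Relative errors:

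| Hazard, loss | E | *Without*, L = 20% | *Missing*, L = 20% | *Without*, L = 5% | *Missing*, L = 5% |
|---|---|---|---|---|---|
| Constant, early | 0.0129 | -16.8% | +3.7% | -4.2% | +0.8% |
| Constant, even | 0.0406 | -9.9% | +11.5% | -2.5% | +2.4% |
| Early-peaking, early | 0.0266 | -13.3% | +7.6% | -3.3% | +1.6% |
| Early-peaking, even | 0.0506 | -7.4% | +14.4% | -1.8% | +3.1% |

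**Limits at L = 20%.** A separate run with true risks of 2%, 5% and 10% and extreme loss times gives 0 to -20% for *Without* and 0 to about +24% for *Missing*. The ends belong to loss at Day 0 and loss just before Day 90. The Day 0 end is only a bound, because the SAP's FAS requires a post-treatment assessment.

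**Ratio between arms.**
- Equal 20% loss, true ratio 0.80: 0.800 under *Without*, 0.800 to 0.802 under *Missing*.
- Loss of 25% (treatment) v 15% (control), true ratio 1.00, early loss: 0.90 (constant hazard) or 0.93 (early-peaking) under *Without*.
- The same imbalance with even loss: 0.95 or 0.96 under *Without*.
- Under *Missing*, the imbalance gives 1.02 to 1.08 across the four cells.

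**The case against.** A reader might infer that the reported incidences will be off by 10-17% because the plan expects 20% dropouts. The documents do not support this, for two reasons.

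- The 20% is a sample-size allowance. Protocol 5.3 and SAP 4.5.3 count any non-completion as a dropout, including adverse events, lack of efficacy and poor compliance. Many of these patients can still be observed for events. Protocol 5.3 asks for endpoint follow-up after withdrawal where possible. Protocol 6.1.6.3 asks patients who stop the drug to complete the 3-month endpoint follow-up, and asks sites to make every effort to reach those lost. Only patients who cannot be reached create the problem.
- The size and sign depend on loss timing, hazard shape and the denominator rule, none of which is given.

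A reader might also infer that the treatment comparison is biased. That needs loss that differs by arm or is related to risk. The trial is double-blind, and the 25% v 15% split above is only an illustration.

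It can also be said that a fixed 90-day proportion is a recognised choice for short follow-up. At 8% risk, the absolute error at 20% loss (0.3 to 1.3 points) is smaller than the sampling half-width in one arm: 1.96 × √(0.08 × 0.92 / 984) = 1.7 points.

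These points limit the size, but the gap stands. The protocol names a cumulative incidence, the SAP names no estimator that delivers it under incomplete follow-up, and the two available readings err in opposite directions. In the even-loss example, the unwritten rule alone moves the result from 7.2% to 8.9%.

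**Conclusion.** The concern holds in limited form. Both event endpoints are crude 90-day proportions with no censoring and no rule for event-free leavers. If all 20% were lost to event follow-up, the relative error would be about -7% to -17% (*Without*) or +4% to +14% (*Missing*); at 5% loss it would be about 1-4%. These figures rest on an assumed 8% risk, constant or early-peaking hazard, early or even loss, and loss independent of risk. The error falls on the absolute incidence in each arm; with equal, unrelated loss the risk ratio barely moves. The primary endpoint and sample size are not affected. It should be corrected in the SAP, because a better estimator is available at small cost.

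**What to change.** - **Clinically dated events** (ischaemic stroke, TIA, haemorrhagic stroke, myocardial infarction, vascular death and the combined vascular endpoint): analyse time from randomization to first event, censored at last contact or Day 90. Report Kaplan-Meier or cumulative-incidence estimates by arm, with other death as a competing event, and a log-rank test or Cox hazard ratio.
- **Simple proportions**: keep the planned tables as description, and state how patients who leave event-free are counted.
- **New MRI lesions at the last visit**: these have no onset date, so time-to-event analysis does not suit the full ischaemic composite. Report them separately, as a proportion among patients scanned; protocol 8.4 specifies the Day 90 MRI sequence for radiology-subgroup centres.
- **Event dates**: confirm that the CRF endpoint table records them. Protocol 9.1.2.1 lists a classification table and supporting records but does not mention a date. Under protocol 10.4.2, ischaemic stroke, TIA and myocardial infarction are not recorded as adverse events, so adverse event onset dates cannot fill the gap.

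The cost is SAP wording and a few more tables, provided that the dates exist. The downside is that censoring must be assumed non-informative. That is still a weaker assumption than no events in unobserved time.

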5.3 Safety index

- 1. Incidence of adverse events
- 2. Clinical laboratory index

Blood routine test (hemoglobin, red blood cells, white blood cells, platelets), routine urine test (urine protein, urinary white blood cells, urinary red blood cells), serum biochemistry (alanine aminotransferase, aspartate aminotransferase, alkaline phosphatase, total bilirubin, glutamine, urinary nitrogen, creatinine, total bilirubin, blood glucose, total cholesterol, triglycerides, low density lipoprotein, high density lipoprotein), four items of blood coagulation (PT, APTT, TT, FIB)

- 3、ECG
- 4. Physical examination

Include: Vital signs (systolic pressure, diastolic pressure, heart rate, pulse, body temperature), examination of body systems (general condition, skin, superficial lymph nodes, head and neck, heart, lung, abdomen, nervous system, urogenital system, spine and limbs and others).

6. Statistical analysis

6.1 Analysis set

Efficacy analysis is conducted on the basis of FAS and PPS. Analysis on baseline demographic data will be performed on the basis of FAS and safety evaluation on SS.

6.1.1 Full analysis set (FAS)

Full analysis set (FAS) or modified intention-to-treat (ITT): Set of all the patients who underwent randomization, given any treatment, and underwent any posttreatment assessment. When main indexes of curative effect are missing, the set should be supplemented with last observation carried forward (LOCF) on the basis of intention to treat (ITT). Comparability analysis and the missing value of secondary effect indexes don't need data-carry-forward. Take analysis on actual data in FAS.

FAS population is the main population for curative evaluation in this study.

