5.1. Inclusion criteria

- 1. Ischemic stroke within 72 h after onset, confirmed by MRI or CT;
- 2. Age 35–75 years, inclusive;
- 3. Patients with the first attack or patients with stroke history (modified Rankin Scale score 0-1);
- 4. Clear signs of localization of nervous system, NIHSS score 4 to 22;
- 5. Patient or proxy has signed *Informed Consent Form*.

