11.4 Randomization

11.4.1 Randomization method

Method of centralized dynamic randomization, with each center competing for enrollment. The centralized randomization procedure will be performed using the Interactive Web-based Randomization System (IWRS) provided by Peking University Clinical Research Institute. The principal investigators at each study center will have their own unique login credentials, ensuring the security and integrity of the login system. After screening each eligible subject at all participating centers in this study, the investigator will log in to the randomization system with their accounts, input relevant information about the subject and obtain the drug packaging number for that subject. The investigators will administer the relevant drug based on the drug

packaging number. Subjects will be randomized into treatment and control groups based on stratification factors, which include:

- 1. Whether thrombolytic therapy has been administered: Yes, No
- 2. NIHSS Score: 4–7 points, 8–14 points, 15–22 points

The randomization method is the Pocock and Simon minimization algorithm. Patients must initiate the study treatment within 24–48 hours after randomization. This study employs non-repeated randomization.

12 Statistical Analysis

After the study protocol is finalized, statistical professionals will collaborate with the principal investigator to develop the statistical analysis plan. The statistical analysis software used is SAS® 9.2 software (Software installation point authorization code: 11202165). The sample size calculation software used is PASS 11.

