12.1 Analysis population

The study population is divided into the following categories:

- Full Analysis Set (FAS): The set of subjects according to the Intention To Treat (ITT) principle. It refers to the dataset composed of all subjects who participated in the randomization process and underwent baseline assessments. For subjects for whom complete efficacy assessments are not observed, data truncation will be carried out following the Last Observation Carried Forward (LOCF) principle.
- Per-Protocol Set (PPS): It refers to the collection of cases that meet the inclusion criteria, do not meet the exclusion criteria, and complete the treatment regimen. This includes cases that adhere to the study protocol, exhibit good compliance, and complete the specified CRF entries for analysis (PP analysis).
- Safety Set (SS): It refers to the set of all randomized subjects who received the study drug and had at least one safety assessment after baseline.

The efficacy analysis will be conducted based on the FAS and the PPS. The analysis of all baseline demographic data will be conducted based on the FAS, and safety assessment will be performed on the SS.

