4.5.1 Inclusion criteria

- 1. Have onset of ischemic stroke within 72 hours, and be diagnosed by CT/MRI;
- 2. At age of 35to 75;
- 3. First onset or with past history of ischemic stroke, but have recovered before this onset, that is with mRS score <1;
- 4. With clear nervous system orientation sign, and national institutes of health stroke scale (NIHSS) ≥4 and <22:
 - 5. The patient or his (her) legal representative has signed informed consent before the start of study.

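### The SAP narrows the protocol's full analysis set by two post-randomisation conditions, so randomised patients with no dose or no later assessment leave the primary analysis

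*Combined protocol and SAP*

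**What the plan says.** Protocol 12.1 sets up the FAS under the ITT principle: "It refers to the dataset composed of all subjects who participated in the randomization process and underwent baseline assessments". Where efficacy data are incomplete, "data truncation will be carried out following the Last Observation Carried Forward (LOCF) principle".

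SAP 6.1.1 uses the same name, labels the set a modified ITT population, and defines it as "Set of all the patients who underwent randomization, given any treatment, and underwent any posttreatment assessment". It then states that "FAS population is the main population for curative evaluation in this study". For a missing primary outcome, "the set should be supplemented with last observation carried forward (LOCF) on the basis of intention to treat (ITT"). The only sensitivity analysis of the primary endpoint (SAP 6.2.4) moves the cut-off to mRS ≤2. None changes the population.

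Two timing rules bear on who is affected. On dosing, Protocol 11.4.1 says: "Patients must initiate the study treatment within 24–48 hours after randomization" (SAP 4.2 has the same window). The first scheduled visit after randomisation is Day 7 ± 2 (flowcharts in Protocol Appendix 1 and SAP 4.1.3).

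A secondary mismatch concerns eligibility. For patients with an earlier stroke, SAP 4.5.1 requires recovery before the present onset, "that is with mRS score <1", and it sets NIHSS at ≥4 and <22. Protocol 5.1 admits patients with "stroke history (modified Rankin Scale score 0-1") and NIHSS from 4 to 22.

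**The concern.** Both SAP conditions are met or missed after randomisation. Failing the second is linked to outcome, because a patient who dies soon after the first dose may never be assessed again. Removing such patients raises the observed success rate of whichever arm loses more of them, and the comparison is then no longer between the groups as randomised.

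The two documents also give one name to two different populations for the primary test. Unless they are reconciled before unblinding, the choice between them could be made once results are known.

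The eligibility mismatch matters less. The per-protocol set (SAP 6.1.2) is built on meeting the inclusion criteria, so its membership depends on which version of those criteria is applied.

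**Working it through.** **1. Who is in which set.** Baseline mRS, NIHSS and Barthel Index are scored at Visit 1 (Protocol 8.1), so in practice the protocol FAS is everyone randomised.

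| Randomised patient | Protocol FAS | SAP FAS |
|---|---|---|
| Never dosed | In | Out |
| Dosed, then dies or is lost with no later assessment | In; LOCF carries the baseline mRS | Out |
| Dosed, worsens, assessed at an event visit (Protocol 8.6) | In | In |
| Dosed, withdraws with a final assessment (Protocol 5.3) | In | In |
| Dosed, stops drug, completes the 3-month follow-up (Protocol 6.1.6.3) | In | In |

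Only the first two rows differ. The SAP does not define a post-treatment assessment, so a patient who dies after one dose, with only an adverse-event report on file, could be classified either way.

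**2. The plan's own figure.** Inputs from Protocol 4.2 and SAP 4.4: 40% against 47%, two-sided α = 0.05, power 80%, 1:1 allocation, 20% dropout.

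n = [1.96·√(2·0.435·0.565) + 0.842·√(0.40·0.60 + 0.47·0.53)]² / 0.07² = 787 per arm (rounded up).

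787/(1 − 0.20) = 984 per arm, 1,968 in total. Both match the plan. Power is 80.0% with 787 per arm and 88.0% with all 984.

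**3. Effect of exclusion.** The documents give no rate of non-dosing or of missing assessments, so every rate below is assumed. Suppose a fraction f of an arm is excluded and all of them are non-responders. The observed rate is then p/(1 − f).

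*No true effect (40% in both arms), unequal exclusion:*
- 2% against 1% (about 20 and 10 patients): 0.40/0.98 = 40.8%; 0.40/0.99 = 40.4%; shift 0.4 points.
- 4% against 2% (about 39 and 20 patients): 0.40/0.96 = 41.7%; 0.40/0.98 = 40.8%; shift 0.85, about 0.9 points.

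The shift favours the arm that loses more patients. If that were the Tongxinluo arm, the one-sided rejection rate would be 1 − Φ(1.96 − d/SE), where d is the shift and SE = √[p_T(1 − p_T)/n_T + p_C(1 − p_C)/n_C]. For 2% against 1%, d = 0.0041 and SE = 0.0223, which gives 3.8% against a nominal 2.5%. For 4% against 2%, d = 0.0085 and SE = 0.0225, which gives 5.7%. A more extreme 5% against 1% shifts the difference by 1.7 points and gives 11.4%. If the placebo arm lost more patients, the shift would run against Tongxinluo.

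*Planned effect (40% against 47%), equal exclusion:* 1% per arm gives 40.4% and 47.5% (difference 7.07 points). 5% gives 42.1% and 49.5% (7.37). 10% gives 44.4% and 52.2% (7.78). Balanced exclusion therefore also enlarges the apparent effect.

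**4. What LOCF does with deaths.** The mRS in Protocol Appendix 2 runs from 0 to 5 and has no level for death. LOCF would carry the last score before death. Restoring the protocol FAS therefore does not by itself make a death a failure.

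**5. Eligibility.** The SAP's NIHSS limit of <22 conflicts with its own 15–22 stratum (4.2) and with the NIHSS 4–22 basis of its sample size (4.4). Its pre-stroke mRS limit conflicts with Protocol 5.1.

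**The case against.** A reader might infer that every early death, deterioration or withdrawal leaves the SAP's analysis. The documents do not support that. The SAP asks for any assessment after treatment, not for an mRS and not for the Day 7 visit. Protocol 8.6 requires documentation within 72 hours of a new neurological event, including mRS, NIHSS and Barthel Index. Protocol 5.3 asks for a final assessment at withdrawal, and 6.1.6.3 asks for the 3-month endpoint follow-up after drug is stopped. Even some dosed early deaths might stay in if the mandatory adverse-event report (Protocol 10.4.2) were counted as an assessment. This objection stands, and it limits the point to the first two rows of the table.

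The SAP also openly labels its set as modified, is written after the protocol (Protocol 12), and names one main population. On that view there is an unexplained change rather than two competing analyses. That is fair, but neither document says which governs.

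The size is assumed and small against the planned 7 points. Under double blinding, exclusions before the first dose have no evident route to imbalance. That stands too, although blinding does not prevent outcome-linked loss once dosing has begun.

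On eligibility, a reader might infer that properly enrolled patients with NIHSS 22 will be struck from the per-protocol set. The SAP's own strata suggest that a ≤ sign was lost in translation or extraction. The mRS limit applies only to patients with an earlier stroke, the blind review (Protocol 13.3) includes an eligibility check, and the per-protocol set is secondary.

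**Conclusion.** The two definitions of the primary efficacy population conflict, and the SAP's version conditions on events after randomisation without explanation and without an all-randomised sensitivity analysis. The patients affected are those never dosed and those dosed but never assessed again, chiefly some early deaths.

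The shifts of 0.4 to 0.9 points are illustrations, not estimates. They assume that all excluded patients are non-responders and that one arm loses twice as many as the other, at rates the documents do not give. It would be wrong to read them as a known bias towards Tongxinluo, because the direction cannot be determined. What is certain is the conflict itself, and it should be settled before unblinding. The eligibility mismatch is a lesser matter that touches only the per-protocol set.

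**What to change.** - In SAP 6.1.1, make the protocol FAS the primary efficacy set: all randomised patients with a baseline assessment, analysed as randomised, whether or not they were dosed or assessed afterwards.
- Keep the dosed-and-assessed set as a named sensitivity analysis, and define what counts as a post-treatment assessment.
- Add an explicit analysis rule that death before Day 90 counts as not achieving mRS ≤1. This rule is new: it appears in neither document and should be presented as an addition.
- Reconcile SAP 4.5.1 with Protocol 5.1 and with the SAP's own 15–22 stratum, so that the per-protocol set rests on the criteria used for enrolment.

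The cost is SAP wording only. No further data are needed and the sample size does not change.
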